A Hybrid Type-I Implementation-effectiveness research design will allow the research team, comprising investigators with expertise in intervention development, efficacy and effectiveness research, and implementation science, to simultaneously investigate the effectiveness of *SAH-C* in a military population while identifying any barriers to implementation that would need to be addressed before *SAH-C* could be successfully implemented on a larger scale. The study site for this proposed effort is Joint Base Lewis McChord, Washington.

The primary hypotheses are that those receiving *SAH-C* will evidence greater reductions in physical and psychological IPV, and greater increases in relationship satisfaction, relative to those receiving *Supportive Prevention* across the follow up time points.

(c) Specific Objectives.

AIM 1: To test the effectiveness of *SAH-C* for military couples on an installation, we will conduct a randomized trial comparing 10 sessions of *SAH-C* to 10 sessions of *Supportive Prevention (SP)* under representative conditions, with 140 couples who are at risk for the development of IPA (risk is established if at least one member of the couple reports at or below a score of 100 on the Dyadic Adjustment Scale (DAS), a cutoff score used to distinguish relationship distress, or they report the presence of psychological aggression in the past three months). This aim will be fulfilled by accomplishing the following subaims:

Subaim 1.1: To compare the frequency of physical IPA perpetration of both members of the couple across conditions as reported by service members and their collateral relationship partners at post-intervention and two 3-month follow ups.

Subaim 1.2: To compare the frequency of psychological IPA perpetration of both members of the couple across conditions as reported by service members and their collateral relationship partners at post-intervention and two 3-month follow ups.

Subaim 1.3: To compare relationship satisfaction across conditions as reported by service members and their collateral relationship partners at post-intervention and two 3-month follow ups.

AIM 2: To explore differences in compliance factors across conditions, we will compare session attendance.

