One strategy to bridge the implementation gap is to capitalize on both researchers' and stakeholders' knowledge to ensure fit between the intervention training, provider needs, and organizational context. Recently described by Curran and colleagues,⁴⁸ a hybrid Type I implementation-effectiveness research design allows for the conduct of a rigorous effectiveness trial while simultaneously investigating potential barriers and facilitators to implementation. This information can guide future refinements to the intervention to improve the fit between the intervention and the service setting and inform the selection or development of an appropriate implementation strategy. Hybrid research methodologies, by increasing the efficiency of the research necessary to facilitate implementation, can reduce the time between the identification of effective interventions and their introduction into service systems and settings. The proposed design will position the research team and its operational partners to rapidly act on findings to enhance the effectiveness or fit of *SAH-C* in military settings if needed, and to roll the intervention out more broadly if our findings warrant doing so.

(c) Outline of *SAH-C*

SAH-C derives from a unique fusion of interventions for trauma and IPA, integrating elements of cognitive processing therapy for PTSD,³⁹ couples therapy for PTSD,⁴⁰ and a cognitive behavioral intervention for IPA.⁴¹ *SAH-C* consists of 10 two-hour weekly sessions, led by a provider. This was the minimum length deemed necessary to incorporate components addressing the proposed IPA mechanisms and is consistent with the briefest IPA interventions.⁴² During each session, couples are provided assignments to practice skills together and to assist with the consolidation of material. A group couples format is used because group cohesion among clients appears to be associated with IPA prevention.⁴³ Group interventions also use less time and resources than individual-based interventions. In this psychoeducation intervention, the couples participating in the program are the learners. What follows is a brief outline of each of the 10 *SAH-C* sessions.

Session 1: Introduction and Welcoming

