The ongoing intervention questionnaire has been adapted from the United States Army Medical Command (MEDCOM) behavioral health intake form. The two questions asked request participants to explain the types of services they currently receive (i.e., alcohol and drug, community behavioral health, chaplains, etc.) and the type of therapy they are attending (i.e., individual, couples, family, or group).

The suicidality measure is comprised of items from other scales. Items 1-4 are from the Depression Symptom Index-Suicidality Subscale by Metalsky & Joiner⁸⁴, 1997; 5-6 created by Joiner and Gutierrez, 7-8 from the Beck Scale for Suicide Ideation by Beck & Steer, 1991⁸⁵, 9-11 from the Beck Hopelessness Scale by Beck, Weissman, Lester, & Trexler, 1972⁸⁶, and 12-16 from the Interpersonal Needs Questionnaire by Van Orden et al., 2012⁸⁷. This assessment examines thoughts about killing oneself, the number of suicide attempts since the last suicide risk assessment, wish to live/die, and feelings of belongingness within relationships. This suicide assessment was recommended by Centers for Disease Control suicide researchers, is currently being used within DoD, and derives from 5 different validated assessments.

The REDCap survey will consist of a demographic questionnaire, a Partner Contact form, the *PTSD Checklist* (PCL)⁸¹, the *Alcohol Use Disorders Identification Test* (AUDIT)⁸², the Childhood Trauma Questionnaire (CTQ)⁸³, a suicidality measure, the *Revised Conflict Tactics Scale-2* (CTS-2),⁴⁴ the *Multidimensional Measure of Emotional Abuse* (MMEA)⁸⁰, the *Dyadic Adjustment Scale* (DAS)⁶⁹, an ongoing intervention questionnaire, and a Post-intervention Satisfaction assessment.

During baseline assessment, the demographics questionnaire, partner contact form, CTS-2 (time one), DAS, MMEA, PCL, AUDIT, ongoing intervention assessment, the suicidality measure, and CTQ will be given to the participants. At the post-intervention assessment, the partner contact form, CTS-2 post-intervention, DAS, MMEA, PCL, AUDIT, ongoing intervention assessment, the suicidality measure, and post-intervention satisfaction measures will be given. At the 3-month follow up, partner contact, the CTS-2 post-intervention, DAS, MMEA, AUDIT, ongoing intervention assessment, the suicidality measure, and PCL will be assessed.

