assumed to be a function of observed covariates and previously measured outcomes, but not unobserved outcomes). Based on such considerations, this type of an approach has been recommended for analyzing outcomes in prevention trials as it is generally more powerful than traditional repeated measures analyses of variance.⁹¹ In the current project it is of interest to model person-specific effects (i.e., time course for each participant), as well as the variation of responses between individuals. In addition, because of the suspected intraclass correlation between individuals nested within intervention groups, couples, and perhaps intervention site, these variables will be treated as fixed effects in the analyses. Time will be modeled as a random effect, and condition (*SAH-C* and *ST*) will be a fixed effect. Change in intervention outcomes over time and differences between the conditions over time (intervention by time interactions) will be examined. The primary effect size for the study will be derived from the random regression analyses, and specifically the intervention by time interaction, which will compare the two groups across intervention and follow ups. There are covariates that are *a priori* hypothesized to be associated with intervention outcomes, including socioeconomic status and education, and these will be included in follow-up analyses to significantly reduce error variance.

(e) Exploratory Analyses

Differences between the two group conditions in participant intervention compliance (Aim 2) will be explored by examining condition differences in session attendance using ANOVAs.

(f) Qualitative Analytic Strategy and Data Integration

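### The primary condition-by-time model names no adjustment for the baseline outcome, so for psychological IPA and DAS it gives up a small amount of precision that could be had free

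*Combined protocol and SAP*

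**What the plan says.** Section (d) Primary Data Analyses specifies random-effects regression and states: "The primary effect size for the study will be derived from the random regression analyses, and specifically the intervention by time interaction". Condition is a fixed effect, and "Time will be modeled as a random effect". For intervention group, couple and possibly site, the section says "these variables will be treated as fixed effects in the analyses". The only covariates it names are those "including socioeconomic status and education, and these will be included in follow-up analyses to significantly reduce error variance", so they do not enter the primary model. It mentions neither the baseline score as a covariate nor a constraint of equal arm means at baseline.

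The baseline data exist. Section (b) Independent variables and Dependent (outcome) variables lists the measures: "During baseline assessment, the demographics questionnaire, partner contact form, CTS-2 (time one), DAS, MMEA, PCL, AUDIT". Section (1)(b) states the hypothesis as greater change "across the follow up time points", and the subaims in (1)(c) are assessed "at post-intervention and two 3-month follow ups". Under Preliminary Studies, the prior randomised trial is reported with ANCOVA controlling for baseline scores.

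**The concern.** With the arms free to differ at baseline, or with couple entered as a fixed effect, a condition-by-time interaction compares changes from baseline. That contrast subtracts the whole baseline score, whereas the efficient weight is the baseline-to-follow-up correlation. When that correlation is below 1, as in the range that (g) Power Analysis reports, and variances are equal, the change contrast carries avoidable noise.

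At stake is the width of the main interval for psychological IPA and DAS. A chance baseline gap would also leave a residue. One standard error at 70 couples per arm, before any urn balancing, is √(2/70) = .169 SD. At r = .70 this moves a change contrast by (1 − .70) × .169 = .05 SD in favour of the arm that starts worse. Over repeated randomisations the shift averages zero, so this is imprecision and not bias.

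**Working it through.** **Inputs.** From (g) Power Analysis: r = .70 (observed range .53 to .90, CTS-2 only), group ICC about .05, d = .5, 20% attrition, two-sided .05. From (5)(c): 14 groups of 5 couples per arm. After attrition this leaves 56 couples per arm, 4 per group. Visit times of 0, 2.5, 5.5 and 8.5 months are inferred from "10 two-hour weekly sessions" and the two 3-month follow-ups.

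**Assumed.** Equal variances; one score per couple; a group component that is constant over the follow-ups and absent at baseline; random-slope SDs s of 0, .04 and .08 per month, in baseline SD units.

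**The plan's own figure.** The plan claims power above .9 for 280 individuals. Treating 112 per arm as independent, with one measurement and d = .5, gives .96. With 56 couples per arm, a one-follow-up change contrast and no group clustering, power is .92. The claim is reproducible on these readings.

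**Group term.** With 4 couples per group the design effect is 1 + 3 × .05 = 1.15, which adds .15 to the per-couple variance of a follow-up mean. Groups form after randomisation, so baseline scores cannot remove this part. It is added to both contrasts.

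**One follow-up, s = 0.**
- Change: 2(1 − r) + .15 = .60 + .15 = .75.
- Adjusted: 1 − r² + .15 = .51 + .15 = .66.
- Ratio .66/.75 = .88, a 12% cut. At r = .53 it is .869/1.09 = .80 (20%); at r = .90, .34/.35 = .97 (3%).
- At the last visit, slope variance adds 8.5²s² to both. The ratio is .776/.866 = .90 at s = .04 and 1.122/1.212 = .93 at s = .08.

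**Average of three follow-ups, s = 0.**
- Change: (1 + 2r)/3 + 1 − 2r + .15 = .80 − .40 + .15 = .55.
- Adjusted: (1 + 2r)/3 − r² + .15 = .80 − .49 + .15 = .46.
- Ratio .836, a 16% cut.

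**Linear interaction.** This is generalised least squares, common against free baseline mean. The covariance is r, plus (1 − r) on the diagonal, plus s²·tᵢ·tⱼ, plus .15 between post-baseline visits. The effect is scaled so that d = .5 is reached at the last visit. Power uses the noncentral t with 110 df and noncentrality .5/√(2v/56), where v is the per-couple variance.

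| Contrast (r = .70) | s | v, free → common baseline | Variance cut | Interval narrower by | Power |
|---|---|---|---|---|---|
| Linear | 0 | .628 → .575 | 9% | 4.4% | .91 → .93 |
| Linear | .04 | .744 → .690 | 7% | 3.7% | .86 → .88 |
| Linear | .08 | 1.091 → 1.037 | 5% | 2.5% | .71 → .73 |
| One follow-up | 0 | .75 → .66 | 12% | 6.2% | .86 → .90 |
| Average of three | 0 | .55 → .46 | 16% | 8.5% | .94 → .97 |
| Average of three | .04 | .598 → .508 | 15% | 7.8% | .92 → .96 |
| Average of three | .08 | .744 → .654 | 12% | 6.2% | .86 → .90 |

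**Sensitivity to unequal variances.** With k = follow-up SD / baseline SD, the single-visit ratio (no group term) is k²(1 − r²)/(k² + 1 − 2rk). At r = .70:
- Table 2, veteran DAS, 28.76 to 44.64: k = 1.552, ratio 1.229/1.236 = .99, a cut of about 1%.
- Table 1, veteran psychological CTS, SAH arm, 25.9 to 17.0: k = .656, ratio .220/.512 = .43, a cut of 57%.
- The same measure in the comparison arm, 26.7 to 25.9: k = .970, ratio .480/.583 = .82, a cut of 18%.

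**Fixed couple terms.** With 140 couple indicators, condition at baseline is a sum of indicators already in the model. For 28 groups of 5 couples over four visits the design has rank 140 + 3 + 3 = 146, with or without a baseline condition term. A common baseline mean therefore constrains nothing while couple is fixed. The planned interaction itself remains estimable: adding condition by linear time raises the rank from 143 to 144.

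**The case against.** The strongest reply is that the gain is small and its size poorly known. Scaling both contrasts by the same design effect would give cuts of 14% (linear), 15% (one follow-up) and 22.5% (average) at s = 0. A reader might infer gains of that order, but they treat group variation as if baseline scores could remove part of it. The objection is right, and the smaller figures are used here. It is also right that r comes from CTS-2 reports pooling physical and psychological IPA, that its use for MMEA and DAS is an assumption, and that the SDs in Tables 1 and 2 put the single-visit gain anywhere from about 1% to over 50%.

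Second, the plan implies free baseline means but does not state them, and the word fixed for couple may be a slip in a section that calls for random-effects regression. Both are possible. The text still names no baseline adjustment, so the point survives as a request to specify one.

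Third, a reader might infer from the hypothesis wording that the interaction is the wrong primary effect and should give way to a follow-up average. The documents do not support that. Section (d) says the interaction compares the arms across intervention and follow-ups, so a change of contrast is optional and separate.

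**Conclusion.** The point holds as a modest precision gain available from data already collected. Under the stated assumptions at r = .70, the variance falls by about 5% to 9% for a linear interaction, about 12% for one follow-up and 12% to 16% for the three-visit average. Power rises by about 2 points for the linear interaction (for example .86 to .88 at an assumed slope SD of .04) and by 3 to 4 points otherwise. The direction is secure under equal variances; the size is not, and confidence in it is medium.

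Two stronger readings should be resisted. The primary analysis is not biased or invalid for want of this adjustment, since randomisation makes the change contrast valid. Nor do these figures show the trial to be underpowered: power above or below .9 here turns mainly on the assumed slope variance and the contrast chosen. Physical IPA is outside the point, because couples reporting it in the past three months are excluded at entry and its baseline has little usable variation.

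**What to change.** In (d), for psychological IPA and DAS, specify one of two forms:

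- Keep baseline as an outcome row and fit one baseline mean common to both arms. The intervention-by-time interaction can stay as the primary effect.
- Model the three post-baseline scores with the baseline score as a covariate. The effect is then the condition contrast at those visits.

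In either form, enter couple as a random effect, and intervention group as a random effect on post-baseline rows. Fixed couple terms absorb the baseline arm difference and block the adjustment.

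This is a free improvement: no new data or visits are needed. The cost is rewording (d), including its cluster terms, and a few degrees of freedom. Tested on 28 − 2 = 26 group df, one-follow-up power at r = .70 and s = 0 goes from .84 to .88, against .86 to .90 on 110 df.

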Participants (service members and partners) will separately receive remuneration of a \$50 Visa Gift Card or a \$50 check sent to their address for completion of each assessment. Due to military compensation restrictions, and to ensure no conflict, if the service member is active duty, they may only be compensated if they fill out their surveys while on off-duty or on leave status.

(h) Intervention after Completion of Trial

Following the completion of the final assessment, all participants assigned to the *SP* condition will be offered the opportunity to participate in a *SAH-C* group. This participation would be entirely voluntary and would involve no further assessment or remuneration.

(6) Measures

(a) Outcome Measures

Outcome assessments are identical to those from Phase 1, though the assessment window for Phase 2 assessments refers to the prior three months. Data collected will include demographics questionnaire, partner contact form, PCL, AUDIT, Post-Intervention satisfaction, suicidality measure, MMEA⁸⁰, CTS2⁴⁴, ongoing intervention questionnaire, and DAS⁶⁹.

(b) Intervention Compliance Measure

Session Attendance will be measured as the total number of group sessions attended by each client.

(7) Stakeholder Meetings

Stakeholder meetings will be held to discuss study performance and needs of the study, such as discussions related to study recruitment, barriers to participation, and dissemination of research findings.

(c) Intent-to-Treat (ITT) versus “Adequate Dose” Analyses

An ITT philosophy will be strictly adopted. Experts in clinical trials have noted that no consensus exists about how missing data should be handled in ITT analyses, and different imputation approaches result in various potential biases. Thus, there is no single definition of ITT, and the phrase carries different meanings for different researchers.^{87,88} Therefore, every effort will be made to collect complete outcome data for all randomized participants, regardless of their intervention completion. As discussed in section D.3.7., measurement losses are expected to be relatively small due primarily to the use of tracking procedures, as well as the relatively short follow-up assessment periods.

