Inclusion criteria are as follows: (a) couples (heterosexual and same-sex dyads) must be in an intimate relationship; (b) participants and their partners must be over the age of 18, due to our emphasis on adult IPA, and so that all participants will be legally able to provide consent without parental involvement; (c) both members of the couple report no occurrence of physical IPA in the past 3 months; (d) at least one member of the couple reports at or below a score of 100 on the Dyadic Adjustment Scale (DAS), a cutoff score used to distinguish relationship distress, or they report the presence of psychological aggression in the past three months; and (e) both members of the couple provide research consent. Pregnant women are eligible to participate in this study. Research indicates that pregnant women may be at increased risk for intimate partner victimization. Thus, violence prevention interventions may be particularly applicable and important for this group. Potential participants will be excluded on the basis of reading difficulties that preclude valid completion of the assessment instruments.

Gender Inclusion

The couples-based interventions studied make it likely that equal numbers of men and women will participate. However, we will make no exclusions related to gender/gender identity, and same-sex couples are also eligible for participation.

Minority Inclusion

Across the study sites, 70% of potential participants are Caucasian, 20% are African American, and 10% are of another ethnicity.

(b) Sources of Materials

Data will be obtained from subjects from self-report measures completed through the online data collection tool, REDCap. Data will not be collected from routine medical care. All data gathered and analyzed will be obtained for this specific study. Study participation will not be documented in participants' electronic medical records.

(c) Potential Risks

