All appropriate service members aged 18 or older, with partners over the age of 18, reporting no occurrence of physical IPA over the prior 3 months in their relationship will be invited with their partners to participate in a screening to determine appropriateness for group intervention and assess study eligibility. Members of the couple will arrive together but be screened separately to ensure confidentiality and safety. Both members of the couple will be administered the DAS to assess relationship distress, partner contact frequency, the MMEA for emotional abuse, the PCL to screen for PTSD, the AUDIT to screen for alcohol use, the CTQ for child abuse and neglect history, the CTS-2 to assess lifetime history of IPA in their current relationship, the suicidality measure, and the demographics questionnaire. If either participant fails to meet study eligibility requirements, the couple's participation will end. If IPA is reported by either partner, the trained psychoeducational facilitator will separately inform them that they are not eligible for this study, and will assess the victim or victims' perceptions of safety, discuss safety planning with the victim(s) (e.g., packing a small bag with a change of clothes and important papers in the event that s/he needs to escape), and will provide them with local contact information for Victim Advocacy services. Victims will be educated by the Victim Advocate about reporting options which include restricted reporting.

In the event a participant endorses suicidal ideation, the facilitator will conduct safety planning and offer a referral to FAP for additional assistance. If there is imminent threat, the facilitator will inform FAP to conduct a formal suicide assessment or accompany the participant to the emergency room. Additionally, if they have a counselor we will direct them to contact their counselor immediately.

(b) Protection Against Risk

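### Physical IPA is zero at baseline by eligibility, so the hypothesised reduction in it cannot be observed, and the stated power above .9 is not supported for that outcome

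*Combined protocol and SAP*

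**What the plan says.** All references are to the combined protocol and SAP.

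- **Hypothesis**, (1)(b): SAH-C recipients "will evidence greater reductions in physical and psychological IPV, and greater increases in relationship satisfaction" relative to Supportive Prevention (SP).
- **Subaim 1.1**, (1)(c): "To compare the frequency of physical IPA perpetration of both members of the couple across conditions", at post-intervention and two 3-month follow-ups.
- **Eligibility**, (8) Inclusion/Exclusion Criteria: "both members of the couple report no occurrence of physical IPA in the past 3 months".
- **Outcome window**, (6)(a): "the assessment window for Phase 2 assessments refers to the prior three months".
- **Screening**, (9)(a) Screening procedures: each partner completes "the CTS-2 to assess lifetime history of IPA in their current relationship".
- **CTS-2 forms**, (b) Independent variables and Dependent (outcome) variables: the baseline list reads "During baseline assessment, the demographics questionnaire, partner contact form, CTS-2 (time one), DAS, MMEA, PCL, AUDIT" and the post-intervention list includes "the partner contact form, CTS-2 post-intervention, DAS, MMEA, PCL, AUDIT". These are two named versions of the CTS-2, with no window given for either.
- **Primary effect**, (d) Primary Data Analyses: "specifically the intervention by time interaction, which will compare the two groups across intervention and follow ups".
- **Power**, (g): 26% control incidence, 20% attrition, within-subjects correlation .70, d = .5 and two-tailed .05 give power above .9 for IPA frequency with 280 persons (140 couples). The same section says that a single composite index removes the dyadic correlation, and puts the group ICC at about .05.

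**The concern.** The eligibility window and the outcome window are the same three months. Every couple enters with no physical IPA by rule, so one of the primary hypotheses predicts a fall from zero. In (3)(a), the account of the prior trial makes the same point: physical IPA was an exclusion criterion for the Veterans, so no significant decrease was expected. Here the exclusion covers both partners.

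Three things are at stake. First, SAH-C could work and the hypothesised reduction still could not appear. Second, if the lifetime CTS-2 score were entered as baseline, both arms would show an artificial fall to the 3-month follow-up scores. Third, a null result would be read against power above .9, and a constant baseline removes one of the two ways of reaching that figure.

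Psychological IPA and the DAS are not affected by the zero baseline.

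**Working it through.** **Inputs.** From (g): d = .5, r = .70 (observed range .53-.90), 20% attrition, group ICC .05, two-sided .05. From (5)(c): 14 groups of five couples per arm, so 70 couples per arm, or 70 × .8 = 56 after attrition (112 persons). The effect pattern over the four visits is taken as 0, d, d, d, with SD 1 at each follow-up.

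**Method.** Noncentral t with λ = d√(n / (2·k·DE)) and 2n − 2 df. Here n is units per arm, k is the contrast variance divided by the squared contrast effect, and DE is the design effect.

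**k with a zero baseline, r = .70.**
- Linear slope, weights −1.5, −.5, .5, 1.5: effect 1.5d; variance 2.75 + 2(.70)(−.25) = 2.40; k = 2.40/2.25 = 1.07.
- One follow-up: k = 1.00.
- Mean of three follow-ups: k = (1 + 2×.70)/3 = .80.

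**k with a varying baseline, r = .70.**
- Slope: 5(1 − .70)/2.25 = .67.
- One follow-up: 2(1 − .70) = .60.
- Mean of three minus baseline: .80 + 1 − 1.40 = .40.

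**Design effects.**
- Couples: four retained per group, DE = 1 + 3×.05 = 1.15.
- Persons: dyadic correlation .38 (assumption), DE = 1.38. With eight retained per group, the six non-partners add 6×.05, so DE = 1.68.

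| Case | n per arm | Slope | One follow-up | Mean of three |
|---|---|---|---|---|
| *Reproducing above .9* | | | | |
| Independent persons, zero baseline | 112 | .95 | .96 | .99 |
| Couples, varying baseline | 56 | .895 | .92 | .99 |
| *Zero baseline, one composite per couple* | | | | |
| No group ICC | 56 | .72 | .75 | .84 |
| Group ICC .05 | 56 | .66 | .69 | .78 |
| *Zero baseline, one composite per perpetrator* | | | | |
| Dyadic .38 | 112 | .87 | .89 | .94 |
| Dyadic .38, group ICC .05 | 112 | .80 | .82 | .90 |

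The stated figure therefore reproduces in two ways. One treats 280 persons as independent, which does not fit a single composite with no dyadic correlation. The other credits baseline correlation, which a constant cannot supply. The documents do not show which was used.

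**Sensitivity.** Per couple with the group ICC, over r = .53-.90 and attrition 12% (from (5)(g)) to 20%, power runs .64-.87. Without the ICC, only the averaged contrast at r = .53 with 12-15% attrition reaches .90-.91. Per perpetrator, dyadic correlations of .2-.7 give .97-.89 for the averaged contrast, or .93-.84 with the group ICC.

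**Incidence scale.** Assume that 26% is cumulative per couple. The plan gives no treated-arm rate, so d = .5 has to be converted:
- log-odds: 12.4%;
- arcsine: 7.9%;
- binomial SD: .26 − .5√(.26×.74) = 4.1%.

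The usual two-proportion normal approximation with 56 couples per arm, at one time point and without clustering, gives power of .45, .73 and .91.

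**Group terms.** Each of the 28 groups sits in one arm. Fixed group intercepts therefore absorb a condition main effect, but not a condition-by-time term.

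**The case against.** **The hypothesis is comparative, so this is only wording.** Much of this stands. Subaim 1.1 compares frequency after baseline, and (g) speaks of cases that emerge. A reader might infer that physical IPA is untestable. It is not: with both arms starting at zero, the interaction measures the difference in what arises later. The hypothesis wording is still wrong for this outcome, and the CTS-2 conflict is more than wording.

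**Zero holds by rule, not necessarily in the data.** This is true. In the prior trial the Veterans' baseline physical means were .44 and .14 despite their exclusion. A few stray reports would not supply a baseline correlation of .70, however.

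**The couple is not clearly the unit.** This is the strongest objection, and it stands. The single index with no dyadic correlation favours one record per couple. But Subaim 1.1 names both members' perpetration, the CTS-2 description combines partner reports, (d) models person-specific effects with individuals nested in couples, and (g) counts 280. A reader might infer that true power is .66-.84. The documents do not settle that, because the per-perpetrator reading gives .80-.94 at an assumed dyadic correlation of .38, and more if that correlation is lower.

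**Fixed group terms.** A reader might infer that they invalidate the planned interaction. They do not; the problem arises only for a condition contrast averaged over follow-up.

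**Conclusion.** The concern holds in two parts. First, the primary hypothesis of a reduction in physical IPA cannot be observed, because eligibility and the outcome window fix baseline at zero. The lifetime CTS-2 text must be reconciled with that window. This rests on the documents alone.

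Second, power above .9 is not supported for physical IPA. The range is .72-.84 per couple (.66-.78 with the group ICC), or about .87-.94 per perpetrator (.80-.90 with the group ICC). These figures are normal-theory values at d = .5 and r = .70 with 20% attrition; the per-perpetrator ones also assume a dyadic correlation of .38. On the incidence scale, power depends heavily on the treated-arm rate, which is not stated. No single replacement figure follows. In particular, .78 is the normal-theory value for one contrast and one unit, and would not describe a sparse-count or onset model.

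This should be fixed, but it does not invalidate the trial or its planned interaction test.

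**What to change.** 1. Reword the physical-IPA hypothesis as lower frequency or onset after baseline under SAH-C relative to SP.
2. For Subaim 1.1, take as primary effect the condition difference averaged over post-intervention and the two 3-month follow-ups, with no baseline physical-IPA row. Use a model suited to sparse counts or onset, chosen in advance by the sponsor. Handle intervention group by a random effect or cluster-robust errors, since fixed group terms would absorb condition in this contrast.
3. Reconcile the CTS-2 windows across the assessment list, (6)(a), the inclusion criteria and the screening procedures. Do not use a lifetime score as the baseline for change.
4. State whether the composite is per couple or per perpetrator. Recompute physical-IPA power for the chosen model with a zero baseline, the group ICC of .05, any dyadic correlation and an explicit treated-arm rate. Do not present above .9 as applying to physical IPA, and do not insert a fixed substitute such as .78.

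Cost: edits to the hypothesis, analysis, measures and power text, plus the work of choosing a model and rerunning power. No extra couples or data are needed. The stated power is likely to be less favourable. Psychological IPA and the DAS keep their baselines.
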